#### **7.2.2.11. Adverse Events**

Adverse events will be assessed and documented as per the schedule of events (Table 2 and Table 3). This information will be collected at all visits. In addition, subjects/caregivers will be encouraged to report AEs of concern at any time.

In addition, AEs should be evaluated after the Post-Treatment Visit (6 weeks post discontinuation of ataluren) until any drug-related AEs and/or ongoing SAEs have resolved or become stable, whichever occurs later.

**7.2.2.12. Concomitant Medications**

Information regarding any concomitant medications administered, as well as information regarding all non-drug therapies, will be collected throughout the study, as per the schedule of events ([Table 2](#) and [Table 3](#)).

## 8. ADVERSE EVENT ASSESSMENTS

### 8.1. Adverse Event Definitions

#### 8.1.1. Adverse Events

An AE is any untoward medical occurrence associated with the use of a drug (investigational medicinal product) in humans, whether or not it is considered related to the drug. An AE can therefore be any unfavorable and unintended sign (including an abnormal laboratory finding), symptom, or disease in a study subject who is administered ataluren in this study.

For this protocol, untoward medical occurrences that should be reported as AEs include the following:

- All AEs during the course of treatment with ataluren.
- All AEs resulting from medication misuse, abuse, withdrawal or overdose of ataluren.
- All AEs resulting from medication errors such as dispensing or administration error outside of what is described in the protocol.
- Worsening of a preexisting illness.
- Injury or accidents. Note that if a medical condition is known to have caused the injury or accident (a fall secondary to dizziness), the medical condition (dizziness) and the accident (fall) should be reported as 2 separate AEs.
- Abnormalities in physiological testing or physical examination findings that require clinical intervention or further investigation (beyond ordering a repeat [confirmatory] test).
- Laboratory or ECG abnormalities that require clinical intervention or further investigation (beyond ordering a repeat [confirmatory] test) unless they are associated with an already reported clinical event. Laboratory abnormalities associated with a clinical event (e.g., elevated liver enzymes in a subject with jaundice) should be captured in the source documents. Laboratory abnormalities not requiring clinical intervention or further investigation will be captured as part of overall laboratory monitoring and should not be reported as AEs.

A preexisting condition (e.g., allergic rhinitis) must be noted on the appropriate CRF for Visit 1 but should not be reported as an AE unless the condition worsens or episodes increase in frequency during the AE reporting period. Diagnostic and therapeutic non-invasive and invasive procedures, such as surgery, should not be reported as AEs. However, the medical condition for which the procedure was performed should be reported if it meets the definition of an AE. For example, an acute appendicitis occurs during the treatment with study drug should be reported as the AE and the resulting appendectomy should be recorded in the source documents and CRF. If a surgical procedure was planned prior to entry into the study, and the surgery is not performed because of a worsening of a baseline condition, this should not be reported as an AE. Note that, as described in Section 8.1.2, any inpatient hospitalization occurring as the consequence of an AE during the study period should be reported as an SAE.

Each AE is to be classified as serious or non-serious by the investigator using medical and scientific judgment.

### 8.1.2. Serious Adverse Events

An AE, which results in one of the following:

- Results in death (i.e., all deaths on treatment or within 6 weeks after last ataluren administration), including deaths due to progression of DBMD. Any death occurring later than 6 weeks following the last dose need not be reported as an SAE unless it is a result of an event that started within the period covered by the on-study definition. The reported AE should be the event that caused the death.
- Is life-threatening. This refers to an event in which the subject was at risk of death at the time of the event. It does not include an event that, had it occurred in a more severe form, might have caused death.
- Requires inpatient hospitalization or prolongation of existing hospitalization (excluding hospitalizations for administration of ataluren, procedures required by the study protocol, or DBMD-related diagnostic procedures; other planned hospitalizations; or hospitalizations related only to progression of disease). Treatments in the emergency room for procedures such as hydration that do not require admitting the subject to the hospital and observational durations in the emergency room for less than 24 hours do not fall into this category.
- Results in persistent or significant incapacity or substantial disruption of the ability to conduct normal life functions, not related to DBMD.
- Important medical event: These are AEs that might not be immediately life-threatening or results in death or hospitalization but might jeopardize the subjects or might require intervention to prevent one of the other outcomes listed above. Medical judgment should be exercised in deciding whether an AE is serious based on above definition. Examples of such events are intensive treatment in an emergency room or at a home for allergic bronchospasm blood dyscrasias, or convulsions that do not result in inpatient hospitalization, or the development of drug dependency or drug abuse.

All SAEs that occur after any subject has been consented must be recorded on the CRF.

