## **6.2. Study Drug Treatment**

### **6.2.1. Duration of Therapy**

The actual duration of ataluren treatment under this protocol will be subject to the following conditions:

- The subject has the right to withdraw consent and discontinue ataluren at any time.
- The subject's condition substantially worsens after initiating ataluren treatment. In such a case, the subject will be carefully evaluated by the investigator in consultation with the PTC Therapeutics medical monitor. The subject will be withdrawn from treatment if continuing would place them at risk.
- The investigator may withdraw the subject from ataluren treatment, if, in the investigator's clinical judgment, it is not in the subject's best interest to continue or if the subject is not complying with the protocol (ie, per protocol visits, return of unused study drug).
- If the subject is unable to tolerate ataluren, he will be withdrawn from treatment.
- The subject is eligible to participate in another ataluren nmDBMD clinical trial program initiated by PTC Therapeutics.
- This study is discontinued by the relevant regulatory authority and/or PTC Therapeutics.
- Ataluren becomes commercially available.

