### **8.3. Adverse Event Recording**

All AEs (both serious and non-serious) that occur in subjects during the AE reporting period must be recorded, whether or not the event is considered drug related. All AEs are to be recorded in the source documents and the CRF using concise medical terminology; whenever possible terms contained in Medical Dictionary for Regulatory Activities (MedDRA) should be employed.

In addition, the following information should be recorded:

- Indication of whether the event is serious or non-serious (see Section 8.1)
- Relationship to ataluren (see Section 8.4)
- Severity of the event (see Section 8.5)
- Onset date
- Resolution date, or date of death
- Action taken
- Outcome of the event

Classification of the event as serious or non-serious determines the reporting procedures to be followed.

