### 8.7. Adverse Event Reporting Period

The first day of AE reporting will coincide with the day the informed consent is signed. The AE reporting period for this study ends 6 weeks after the last administration of the ataluren.

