### 8.9. Serious Adverse Event Reporting

All SAEs should be reported via the SAE form to PTC Therapeutics within 24 hours of becoming aware of the event(s).

In addition to completing the AE portion of the CRF, the SAE report form must also be completed. The SAE report form should be signed by the investigator; however, if the investigator is unable to sign at the time of the event or within 24 hours, the form should be signed by the clinical staff member reporting the SAE (e.g., the study coordinator). The SAE report form must be emailed or faxed to the PTC Therapeutics Pharmacovigilance Department and to the site IRB/IEC (if required by local regulations) within 24 hours. Follow up information to the SAE should be clearly documented as “follow up” in the SAE report form and must also be emailed or faxed to these same parties. All follow up SAE report forms for the event must be signed by the investigator. Any source documents (e.g., progress notes, nurses’ notes, laboratory and diagnostic test results, discharge summaries) should be redacted so that the subject’s name, address, and other personal identity information are obscured. Only the subject’s study number and initials are to be provided. The information in the AE portion of the CRF and the SAE report form(s) must match or be reconciled. Where the same data are collected, the forms must be completed in a consistent manner. For example, the same AE term should be used on both forms.

In the rare event that the investigator does not become aware of the occurrence of an SAE immediately (for example, if a subject initially seeks treatment elsewhere), the investigator is to report the event within 24 hours after learning of it and to document his/her first awareness of the AE.

The PTC Therapeutics contact information for reporting SAEs is listed below and is also provided in the Study Manual and in the SAE report form.

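### A late-onset death judged related to ataluren need not be reported, and the protocol disagrees with itself on non-fatal SAEs that start after 6 weeks

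*Protocol*

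**What the plan says.** All of the relevant text is in the protocol.

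- **Deaths (Section 8.1.2).** "Any death occurring later than 6 weeks following the last dose need not be reported as an SAE", and the sentence continues "unless it is a result of an event that started within the period covered by the on-study definition". No other exception is given.
- **End of the reporting period (Section 8.7).** "The AE reporting period for this study ends 6 weeks after the last administration of the ataluren".
- **Recording duty (Section 8.3).** It applies to AEs, serious and non-serious, "that occur in subjects during the AE reporting period must be recorded, whether or not the event is considered drug related". It is therefore bounded by the period in 8.7.
- **SAE recording (last sentence of Section 8.1.2).** "All SAEs that occur after any subject has been consented must be recorded on the CRF". This rule has a start but no end.
- **SAE reporting (Table 6 and Section 8.9).** Table 6 requires every serious AE to be both recorded and reported. Section 8.9 requires every SAE to reach the sponsor within 24 hours of awareness. Neither gives a closing date.
- **After the 6-week visit (Section 7.2.2.11).** Evaluation continues "until any drug-related AEs and/or ongoing SAEs have resolved or become stable, whichever occurs later". Section 8.6 likewise continues follow-up of unresolved events.
- **Analysis window (Section 10.4.5.1).** The treatment-emergent definition also stops 6 weeks after the last dose.

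**The concern.** Section 2 gives the study one objective, safety and tolerability, and says the safety profile includes the timing of adverse events and their relationship to ataluren. The synopsis puts the study duration at about 13 years. A serious event that appears late and that the investigator attributes to the drug is exactly the information such a study should pass on. Yet the death rule asks only when the causal event began, and the reporting period closes at the same point with no provision for relatedness.

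The second problem is consistency. Two sites facing the same non-fatal SAE in week 7 after the last dose could act differently, and each could cite the protocol. Under Section 8.11, the sponsor's onward expedited reporting starts only when the sponsor or its agent becomes aware of an event, so an event the site does not report may not reach other investigators.

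**Working it through.** No arithmetic underlies the point. The sample size rests on no formal hypothesis (Section 10.1), and no event rate after discontinuation is given. The check is to apply each rule to each kind of event. I read the on-study period in 8.1.2 as treatment plus 6 weeks, because the same bullet uses that span for reportable deaths.

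| Event | Death rule, 8.1.2 | 8.3 with 8.7 | Last sentence of 8.1.2, Table 6, 8.9 |
|---|---|---|---|
| Death after 6 weeks, causal event began within 6 weeks | Reportable through the exception | Causal event is inside the period | Covered |
| Death after 6 weeks, causal event also began after 6 weeks, judged possibly or probably related | Need not be reported | Outside the period | No end date, but the death is released by the specific rule |
| Non-fatal SAE that began within 6 weeks and is still ongoing | Not applicable | Inside the period | Covered |
| Non-fatal SAE that began in week 7, judged possibly or probably related | Not applicable | Outside the period | Covered |

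The first and third rows raise no difficulty. The second row is the gap: relatedness on the protocol's own scale (Table 4) changes nothing. The fourth row is the contradiction: one pair of sections excludes the event and another group includes it.

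The follow-up provisions do not close the gap. Sections 7.2.2.11 and 8.6 read as continued observation of events already known, not as a duty to collect new ones. Section 7.2.2.11 does show that the plan already treats drug-relatedness as a reason to continue beyond the 6-week visit. The reporting rule does not carry that through.

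The visit schedule can itself produce the case:

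- Reporting closes 6 × 7 = 42 days after the last dose (Section 8.7).
- The Post-Treatment Visit is at 6 weeks ± 7 days (Section 7.2.1.4), that is, days 42 − 7 = 35 to 42 + 7 = 49.
- AEs are collected at that visit (Tables 2 and 3).
- An End-of-Treatment Visit held more than 6 weeks after the last dose removes the need for the Post-Treatment Visit (Section 7.2.1.4), and AEs are collected there too.

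A site can therefore learn, at a protocol visit, of an SAE that began after the period closed, and find no consistent instruction.

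**The case against.** The strongest reply is that the protocol captures more than the death sentence suggests when it is read alone. Much of this stands, and it limits the point in four ways.

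First, a reader might infer that all late deaths are exempt regardless of cause. The exception rules that out: a late death from a toxicity that began on treatment or within 6 weeks remains reportable. Only deaths whose causal event also began after 6 weeks are released.

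Second, a reader might infer that non-fatal late SAEs are exempt in the same way. No sentence says so. The limit is inferred from Sections 8.3 and 8.7, and the open-ended rules point the other way. Section 8.2 also asks for all spontaneously reported AEs, and Section 8.1.1 lists events resulting from withdrawal of ataluren, with no time limit. The text is inconsistent; it is not a clear exemption.

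Third, the death rule is permissive. A site may still report a late death it attributes to ataluren, so one cannot say that such deaths are necessarily lost.

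Fourth, it is tempting to point to boys withdrawn for deterioration, given Section 6.2.1: "The subject will be withdrawn from treatment if continuing would place them at risk". But deterioration that leads to withdrawal has, as a rule, begun on treatment, and Section 8.1.1 makes worsening of a preexisting illness a reportable AE. A later death resulting from it would mostly fall inside the exception. Section 1.1 also says patients usually die of cardiac or pulmonary failure, so many late deaths could be disease progression.

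What remains is that no section expressly requires a new death or SAE that begins after 6 weeks to be reported because it is judged related to ataluren, and the sections do not agree on when SAE reporting ends.

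**Conclusion.** The point holds in two limited parts. For deaths, the release turns on onset time alone, so a late-onset death judged possibly or probably related need not be reported. For non-fatal SAEs that start after 6 weeks, Sections 8.3 and 8.7 conflict with the last sentence of 8.1.2, Table 6 and Section 8.9.

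The size cannot be estimated. The protocol gives neither a death or SAE rate after discontinuation nor the share of such events judged related. Any figure built on assumed survival would describe all late deaths, not the late-onset related ones at issue, so none is offered.

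The conclusion rests on two readings: that the on-study period means treatment plus 6 weeks, and that the follow-up provisions apply only to events already known. It does not call for a longer treatment-emergent window. This is an inexpensive improvement to safety capture and does not threaten the main analysis.

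**What to change.** 1. In Sections 8.1.2 and 8.7, add: *Any death or SAE that the site becomes aware of after the reporting period and judges possibly or probably related to ataluren is reported to the sponsor within 24 hours of awareness.*
2. Align Section 8.3, Table 6, Section 8.9 and the last sentence of 8.1.2 to one rule: the reporting period plus this exception. Amending only 8.1.2 and 8.7 would leave the contradiction in place.
3. List these events separately and leave the treatment-emergent definition in Section 10.4.5.1, and the tables built on it, unchanged.

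The duty arises only when a site learns of an event, so no visit or active follow-up is added and treatment is unaffected. The cost is a few sentences in the next amendment and a few late reports to process.

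### Sections 8.1.1 and 8.1.2 give opposite answers on whether a scheduled admission to treat an on-study adverse event is serious

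*Protocol*

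**What the plan says.** Section 8.1.2 makes an adverse event serious if it meets one of several criteria. The hospitalization criterion opens "Requires inpatient hospitalization or prolongation of existing hospitalization (excluding hospitalizations for administration of ataluren", and the exclusions continue with "procedures required by the study protocol, or DBMD-related diagnostic procedures; other planned hospitalizations". No reference date is attached to the word planned, and nothing is said about why the admission was planned.

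Section 8.1.1, pointing to Section 8.1.2, says that "any inpatient hospitalization occurring as the consequence of an AE during the study period should be reported as an SAE". It makes no exception for scheduled admissions. The same section says that procedures are not themselves adverse events, but that "the medical condition for which the procedure was performed should be reported if it meets the definition of an AE".

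Section 8.7 starts adverse event reporting on the day consent is signed, and "The AE reporting period for this study ends 6 weeks after the last administration of the ataluren". Under Table 6, every SAE goes to the sponsor's pharmacovigilance group within 24 hours of awareness, and no non-serious event does. Section 10.2.1 names safety as the primary endpoint, and Section 10.4.5.1 singles out SAEs for particular attention in the analysis.

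**The concern.** If Section 8.1.2 is followed literally, a new condition that leads to an urgent admission is serious, while the same condition treated at a booked admission is not serious on the hospitalization criterion. Seriousness would then depend partly on how the admission was arranged. Under Section 8.1.1 both are SAEs.

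Two things are at stake. The first is the SAE summary, a main part of the primary safety output. The second is the 24-hour report, which depends on the site's seriousness classification. The study is planned to run about 13 years with about 270 subjects, so admissions booked after enrolment are foreseeable.

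**Working it through.** No arithmetic applies: the plan states no SAE or admission rate, and the question is one of definition. The check takes each kind of admission and reads the two sections side by side.

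1. **Urgent admission for a condition that began on study.** Section 8.1.1: SAE. Section 8.1.2: SAE. They agree.
2. **Admission for a preexisting condition that has not worsened, whenever it was booked.** Section 8.1.1: a preexisting condition is not an adverse event unless it worsens or its episodes become more frequent, so there is nothing to classify as serious. Section 8.1.2: excluded. They agree, but the exclusion does no work here, because every criterion in Section 8.1.2 applies only to something that is already an adverse event.
3. **Admission booked after consent to treat a condition that began or worsened on study.** Section 8.1.1: SAE. Section 8.1.2, read literally: a planned admission, so outside the hospitalization criterion. They conflict.
4. **Admission booked before consent for a condition that then worsens on study.** The worsening is an adverse event under Section 8.1.1, so an admission resulting from it is an SAE. Section 8.1.2, read literally: still a planned admission, so excluded. Again the answer depends on which section the site follows.

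No other section dates a planned hospitalization. The only text that dates a planned procedure begins "If a surgical procedure was planned prior to entry into the study, and the surgery is not performed". It concerns surgery that does not take place, and whether that is an adverse event.

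For cases 3 and 4, two routes remain by which the event is still captured:

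- The condition is recorded as an adverse event with its severity, relationship, action taken and outcome (Section 8.3), so it stays in the adverse event tables.
- It can be serious as an important medical event if it "might require intervention to prevent one of the other outcomes listed above". This rests on medical judgment, so it can recover some of these cases but does not guarantee it.

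**The case against.** The strongest reply is that Section 8.1.1 already gives the right answer. It cites Section 8.1.2 and can be taken as stating how that section is meant to work. Most of the neighbouring exclusions (study drug administration, protocol procedures, diagnostic procedures for the disease) are admissions not caused by a new event, and the planned-hospitalization item can be read the same way. On that reading there is no conflict.

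This is a reasonable account of what was probably intended, but it does not settle the text. Because Section 8.1.1 refers the reader to Section 8.1.2, a site that follows the reference arrives at the exclusion. As case 2 shows, admissions not caused by an adverse event need no exclusion, so read literally the item has effect only on admissions that are.

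Other parts of the reply stand. Section 10.4.5.1 also gives attention to Grade 3 or higher events and drug-related events, so a misclassified event may still be prominent in the analysis. Sections 6.3.1 and 6.3.2 require the sponsor to be told of events leading to dose reduction, discontinuation or interruption, whether or not they are serious.

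A reader might infer three stronger things that the documents do not support:

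- That scheduled admissions do drop out of the SAE tables. They can, but Section 8.1.1 tells sites to report them.
- That dating a plan to before study entry is the protocol's general convention, deliberately left out of Section 8.1.2. The surgery sentence is too narrow to show that.
- That the share lost can be estimated from the corticosteroid complications in Section 1.1. That section reports a high rate only for fractures, says only that gastric ulceration and cataracts are observed, and says nothing about admissions.

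**Conclusion.** The two sections are inconsistent for a scheduled admission to treat a condition that began or worsened on study. Sites can classify the same event differently, and where they follow Section 8.1.2 literally, SAE counts and 24-hour reports are understated unless another seriousness criterion applies. The direction of the error is clear. Its size is not: it depends on how many such admissions occur and how many sites read the exclusion literally, and the documents inform neither. They also do not show that any event has been misclassified.

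This is a reconciliation of two passages, not a flaw that invalidates the safety analysis. It merits correction because it touches the primary safety output and prompt reporting, and the remedy is small.

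**What to change.** In Section 8.1.2, limit the planned-hospitalization exclusion to admissions planned before informed consent for a condition that has not worsened since consent. Consent is the natural reference date because Section 8.7 starts adverse event reporting there. Add a sentence that an admission planned after consent to treat an adverse event is an SAE, which agrees with Section 8.1.1. An admission booked after consent for an unchanged preexisting condition remains outside, because there is no adverse event.

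Notify sites of the clarified rule. Where the eCRF already links an admission or procedure to a non-serious adverse event, query its seriousness. This should be feasible at least for surgical cases, since the appendicitis example in Section 8.1.1 has the operation recorded in both the source documents and the CRF.

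The cost is a clause and a sentence in the next amendment, a site notice, a small amount of query work and possibly a slightly higher SAE count.
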